Oral vs. Topical Antibiotic Therapy for Treatment of Chronic Rhinosinusitis Exacerbations

[name]

[name]

[name], MD, MPA

Background

Chronic Rhinosinusitis (CRS) is a common condition that affects approximately 13 percent of the United States population annually.¹ CRS is a persistent symptomatic inflammation of the nasal cavity and paranasal sinuses due to a variety of host and environmental factors.² According to the American Academy of Otolaryngology-Head and Neck Surgery definition, the diagnosis of CRS requires that patients have at least 2 signs or symptoms of rhinosinusitis (mucopurulent drainage, nasal obstruction, facial pain, pressure, fullness, or hyposmia) for at least 12 weeks as well as documented inflammation on nasal endoscopy or radiographic imaging.³ Treatment is focused on decreasing mucosal inflammation, controlling infection, and improving mucociliary clearance.² Patients who are symptomatic despite medical therapy may undergo endoscopic sinus surgery (ESS). Given the chronic nature of the disease, CRS patients who have undergone endoscopic sinus surgery may continue to have intermittent, acute exacerbations of rhinosinusitis.

There are no FDA approved treatments for acute exacerbations of chronic rhinosinusitis. The mainstay therapy is topical nasal steroids and culture-directed oral antibiotics.⁴ Recent studies suggest that topical antibiotics may provide a more potent and targeted therapeutic option for CRS exacerbations.⁵⁻¹⁵ In post-ESS patients, the open paranasal sinuses result in improved penetration of topical medical therapies, making topical antibiotics an attractive treatment option.¹⁶ Available delivery methods include irrigation, nebulization, atomization, and spray.^{5-14,17} Overall there has been no improvement demonstrated by the use of topical antibiotic sprays, but there has been low-level evidence to support the use of topically irrigated and nebulized antibiotic therapies with overall improvement in patient outcomes.⁴ To our knowledge, there have been no studies comparing nebulizations to irrigations in the treatment of chronic or acute or chronic rhinosinusitis, thus indicating one method of delivery is superior to another. Nebulized therapies have the benefit of a predictably large particle size that results in high intranasal retention.¹⁸ Treatment is well tolerated overall with no major adverse effects reported in the literature.¹⁶ Minor side effects are rare and include local irritation, cough, headache, and sore throat.^{12,16,19} Despite gains in popularity, there is currently little evidence to support the efficacy of topical antibiotic treatments in comparison to oral antibiotics.^{4,17}

Antibiotic treatment of chronic rhinosinusitis is currently based on the organisms that are cultured from the sinonasal cavity. The most prevalent organisms cultured from patients in acute bacterial rhinosinusitis include *Streptococcus pneumonia*, *Haemophilus influenza*, *Moraxella catarrhalis*, and *Staphylococcus aureus*.²⁰ The bacteria involved in chronic rhinosinusitis are similar, with *Staphylococcus aureus* being most prevalent, and *Pseudomonas aeruginosa*, *Haemophilus spp*, and

Streptococcus pneumonia also contributing to the disease etiology.²¹ The microbial contribution to chronic rhinosinusitis is not limited to these pathogens. Considerable interest has been shown in the role of bacterial biofilms to disease. Composition of these biofilms, as well as total bacterial population, has been elucidated using molecular tools with the capability of identifying all bacteria present in a sample.²²⁻²⁴ These techniques have been used previously to compare the bacterial communities of patients with CRS to healthy patients. There have not been any previous studies that have compared patients with acute exacerbations of CRS pre- and post- antibiotic treatment.

Purpose

1. Evaluation of the efficacy of culture-directed sinonal antibiotic nebulizations in treating post-endoscopic sinus surgery CRS patients with active rhinosinusitis compared to conventional treatment with oral antibiotics.
2. Determination of changes in the total bacterial community of the sinonal cavity following oral antibiotic therapy vs. topical antibiotic treatment.

Methods

Subjects

The rhinology clinic at the University of Rochester Medical Center routinely follows CRS patients with nasal endoscopy and with disease-specific quality-of-life questionnaires. Our current clinical standard of practice includes obtaining a sinonal culture directed by nasal endoscopy and making treatment decisions based on the culture results. We will recruit post-ESS CRS patients with worsening symptoms and mucopurulence in the paranasal sinuses seen on nasal endoscopy. Up to 100 potential subjects meeting the defined inclusion criteria will be approached during routine clinic visits with a goal for enrollment of 70 patients. Enrollment is defined as entering the study and receiving treatment. We will screen more patients than will be enrolled, anticipating that approximately 30 patients will not be eligible for inclusion based on their culture results. Patients will not be eligible for inclusion if they are systemically ill at the time of their initial visit or if they require antibiotic treatment prior to finalization of culture data. Justification for a sample size of 70 (35 subjects per treatment group) is based on the assumptions that (1) 90% of patients taking culture-directed oral antibiotics will experience a clinical and statistically significant improvement in Rhinosinusitis Disability Index (RSID) score at the end of therapy, and (2) The non-inferiority limit of topical therapy is 20% of oral therapy. Using a standard deviation of 20% and a power of 0.9, 26 subjects will be required in each treatment group. We will enroll more subjects than required to compensate for any exclusions made once treatment is initiated and for subjects who drop out of the study.

Male and female adults of any race will be considered for inclusion. Mentally and physically disabled persons will be allowed to participate if they exhibit the capacity to consent to participate in the research, to carry out the treatment regimen, and to accurately communicate and record their symptoms, which will be based on the physician's assessment at their initial visit. There will be no exclusion based on economic or educational disadvantage. Prisoners will not be included in the study population due to difficulties coordinating care and administering nebulization therapy.

STUDY00000407

Version date: 03/07/2019

Inclusion criteria

1. Adults (age ≥ 18).
2. Diagnosis of CRS.
3. Worsening sinonasal symptoms.
4. Previous bilateral ESS (including maxillary antrostomy and anterior ethmoidectomy).
5. English speaking.
6. Open sinuses (open middle meatus bilaterally; determined on endoscopy).
7. Positive sinonasal culture (1+ or greater) with sensitivity to Levofloxacin.
8. Individuals must have the ability to understand the requirements of the research and be able to provide consent to participate.

Exclusion criteria

1. Patients < 18 years of age.
2. Treatment with systemic or topical antibiotics within the last 1 month.
3. Pregnant women.
4. Non-English speaking persons.
5. Systemically ill at initial visit necessitating treatment prior to culture data.
6. Allergy to Levofloxacin or other fluroquinolones
7. Patients with a history of long Q-T syndrome.
8. Patients currently taking medications that prolong the Q-T interval.
9. Sinonasal culture with less than 1+ growth.
10. Multiple organisms grown on culture that are not sensitive to a single antibiotic.
11. Patients with ciliary function disorders (cystic fibrosis, Kartagener's syndrome, ciliary dyskinesia).
12. Patients with immunodeficiencies.

Study Design

Sinonasal cultures guided by nasal endoscopy via aspiration with a Tami Sinus Secretion Collector (Medtronic, Minneapolis, MN) will be performed. Aerobic cultures will be obtained, according to the clinical standard of care. If bilateral sinuses appear infected, representative cultures will be taken from each side. After suctioning purulent material, a sterile swab with flocked nylon fiber will be brushed along the mucosa in bilateral maxillary sinuses. The swabs will be placed into separate storage buffers for transport to the laboratory for further molecular analysis. Positive cultures will be defined as 1+ or greater organism growth. Patients with positive cultures will be randomized to one of two treatment groups:

- (1) Daily oral Levofloxacin with twice daily nebulized intranasal placebo for 14 days, or
- (2) Daily oral placebo with twice daily nebulized intranasal topical Levofloxacin for 14 days.

Each nostril will be irrigated with approximately 120 mL of saline solution prior to administration of the nebulized placebo or antibiotic. Patients will not be eligible for enrollment into the study if any organisms are not susceptible to Levofloxacin. Additionally, if bilateral cultures are obtained, the patient will only be eligible for inclusion if all cultures are susceptible to Levofloxacin.

Subjects will enter the blinding process after culture data has been reviewed. A sealed envelope blinded to the investigators selecting either an oral or topical antibiotic will be sent to the participating pharmacy (Professional Arts Pharmacy, Lafayette, LA). This will be based on a separate key that has been blinded to the investigators that will randomly assign a study participant to either an oral or topical antibiotic with the appropriate corresponding placebo. The list will be maintained by the study coordinator. A saline rinse kit (Sinus Rinse, NeilMed, Santa Rosa, CA) and isotonic salt preparation will be supplied to the patient at their initial visit. A nasal nebulizer (NasoNeb, Medinvent, White Bear Lake, MN) and the topical antibiotic with oral placebo or topical placebo with oral antibiotic will be mailed to the subject by the participating pharmacy. Alternatively, instead of the pharmacy shipping to the subject's home, subjects may pick up the appropriately randomized medication regimen from the otolaryngology clinic at Clinton Woods, with the prescription then sent to the participating pharmacy (PAP) to refill the stock. The clinical technician at the clinic in charge of ordering and receiving will be responsible for receipt and storage of the study medication, under the direction and supervision of the PI. The medication will be stored securely in the Clinical Trials office at Clinton Woods. The study drug will be labelled as "Regime A" or "Regime B" corresponding to the randomization scheme in order to ensure that the subject receives the correct medication. The study drug will be dispersed to the subject at the clinic by the PI, or by medically qualified study personnel who receive the culture results (ENT attending, resident or mid-level provider). Patients will be contacted by telephone by study personnel approximately 3 days following delivery of antibiotics to ensure the medications were received and approximately one week later to assess compliance with twice-daily irrigations and nebulizations and to evaluate for any side effects the patient may be experiencing. The participating pharmacy will also contact the patient prior to and following the delivery of medication to instruct the patient on use of the nebulizer, per their current clinical standard of care. A diary will also be given to the patient at their initial visit to assist with compliance.

At the end of treatment, an otolaryngologist blinded to the treatment will repeat nasal endoscopy, cultures, and sinusal brushings to assess response. If there is no mucopurulent drainage within the sinusal cavity, 3 cc of normal saline will be irrigated into the maxillary sinus and sent for culture. Change in Rhinosinusitis Disability Index (RSDI) scores will serve as the primary outcome. The RSDI is a validated, rhinosinusitis-specific 30-item quality-of-life questionnaire.²⁵ It relates the physical, functional, and emotional quality-of-life domains to rhinosinusitis. The survey is set up as an equal-appearing five point scale designated by the words "never", "almost never", "sometimes", "almost always", and "always". Total scores range between 0 and 120 with high scores indicating greater burden of disease. Secondary outcomes will be change in Sinusal Outcome Test (SNOT)-22 scores,²⁶ change in nasal endoscopy findings using Perioperative Sinus Endoscopy (POSE) scores²⁷, post-treatment culture negativity defined as less than 1+ growth of organisms, and change in the total bacterial community following treatment as determined by RNA pyrosequencing. The study participants will be routinely followed in clinic with nasal endoscopy at 2 month intervals for

STUDY00000407

Version date: 03/07/2019

up to 6 months from the time of enrollment, or until the study is closed, to evaluate for disease recurrence or progression.

Molecular Analysis

For the molecular section of the study, samples will be collected via mucosal brushings and as detailed above in the Tami Sinus Secretion Collector. From the Collector, samples will be aseptically divided into two aliquots: one to the microbiology lab for conventional culturing, and one for molecular work. Each sample will be assigned a unique sample identification number (UID) that will be separated from the patient identification. This list will be administered by the study coordinator. Brushings and aliquots of the sample allocated to the molecular work will be transferred into lysis buffer for RNA pyrosequencing ²⁸. The remainder of the sample will be frozen, and maintained at -80C for the remainder of the study.

All of the collected samples of the study will be streaked for anaerobic growth in the research laboratory for speciation. The primary samples will then be analyzed for total bacterial 16s rRNA, allowing comparison of the microbiome within and between pre- and post-treatment in both study arms.

It is anticipated that there may be patients that may not respond to the antibiotic treatment in either the oral or topical antibiotic treatment groups. In this case, the samples that were banked at -80C would be submitted for bacterial RNA transcriptional profiling. Additionally, the correlating banked nasal swab sample would be submitted for human RNA transcriptional profiling. This will allow comparison of the genes expressed by the bacteria that evaded antibiotic therapy in the two treatment arms. Similarly, it will also allow comparison of genes expressed by human endonasal mucosa in response to infection and therapy. Numbers of patients for this part of the study will be determined based on the failure of therapy rate.

After original patient samples have been speciated, and antibiotic sensitivity has been assessed, cultures from the Microbiology Lab will be given the correlating deidentified UID, and frozen at -80C to allow potential future analysis of the isolated strains. Study of these strains will be conducted using the deidentified UID. Samples will be kept at -80 for the remainder of the study.

Timeline

Time (Weeks)	Steps	Notes
Date of enrollment (Week 0)	
 1. Patient questionnaire completed in waiting room. 2. Patient examined with nasal endoscopy. 3. Cultures obtained. 4. Molecular analysis samples obtained and frozen. 5. Consent obtained. 6. Participant given sinus rinse bottle, and saline packets. 	
 • Part of current clinical practice. • Part of current clinical practice. • Part of current clinical practice.
Telephone call/Start of therapy (Day 3-7)	
 1. Antibiotic, placebo and nebulizer mailed to subject, or picked up by subject at the clinic, depending on the subject's preference. 2. Subject instructed on use of nebulizer. 3. Therapy initiated. 	
Telephone call (Start of therapy + 7 days)	
 1. Compliance check. 	
Follow-up (start of therapy +14 days)	
 1. Patient questionnaire completed in waiting room. 2. Patient examined with nasal endoscopy. 3. Cultures obtained 4. Molecular analysis samples obtained and frozen. 5. Therapy terminated. 	
Routine follow-up (every 2 months)	
 1. Patient questionnaire completed in waiting room 2. Patient examined with nasal endoscopy. 	
 • Part of current clinical practice. • Part of current clinical practice.

Data Collection, Analysis and Monitoring

STUDY00000407

Version date: 03/07/2019

Data including patient demographics, endoscopic results, culture data, and quality of life questionnaire scores will be collected and stored on a password protected, encrypted share drive. Any printed data will be stored in the study personnel's office in a locked file cabinet. Only the study personnel will have access to identifying information. Research subjects will be given a unique study number that is stored separately from collected data. The results will be analyzed at the study's completion. A data safety monitoring plan will be ongoing and performed by the investigators. Any adverse events will be recorded and monitored for trends throughout the entire study period. Any serious adverse events will be scrutinized by the principal investigators and study termination will be considered if indicated.

Risk/Benefit Assessment

Risk Category

This is a greater than minimal risk study since it is not necessarily routine to repeat a nasal endoscopy and culture following completion of antibiotic treatment, particularly if the patient is symptomatically improved.

Potential Risk

Potential risks to the subject include mild discomfort and nasal irritation secondary to nasal endoscopy, in addition to any added inconvenience for having to return to the clinic for re-examination. There is a small risk of loss of privacy to the subjects. Genetic information obtained from human subjects will be limited to genes that are currently being expressed.

The remainder of the study is within accordance to the current standards of clinical practice and will not add any additional risk to the patients. The oral and topical treatments proposed are generally safe without any major adverse events reported in the literature.¹⁶ There are no anticipated benefits for the patients participating in the study. Non-participation will not affect the patient's care and they will be treated according to the current standard of care employed by the University of Rochester's Rhinology clinic.

Protection Against Risk

Study participants will be deidentified using a unique study number. All protected health information will be securely stored on a password-protected, encrypted share drive. Any written information will be stored in a locked filing cabinet in the PI's office and will be disposed of in a protected health information bin after 5 years has elapsed.

Safety Monitoring

The principle investigators will be responsible for safety monitoring. All adverse events related to a subject's participation in the research study will be reported to the University of Rochester's Research Subject Review Board (RSRB) as a summary in the annual progress report for the study. Serious, unexpected, and related to the study adverse events will be reported to the RSRB in a

written report within ten calendar days of the study team being notified of the adverse event occurrence.

Sample storage and confidentiality

Collected samples will be assigned a unique sample identification number (UID) and placed into storage at -80° C. It will be the responsibility [name] or his designee to ensure that all samples are stored under appropriate conditions according to type. Samples will be stored indefinitely unless a subject requests, in writing, that their sample(s) be destroyed.

A database will be developed to accompany the sample. Each case will be assigned a unique ID number and all identifiers will then be deleted, except for a single copy (key) containing the ID number, and medical record number. This database would provide clinical and pathological parameters and contain the following information: date of collection, initials of attending physician, gender, date of birth, type of antibiotic used, clinical response to therapy and final microbial diagnosis. It may also contain pertinent medical history and comorbidities, as well as social aspects of history, including tobacco use. Collection of information for the database will be the responsibility of [name]. Study records will be kept in a locked filing cabinet in the Principal Investigator's office in the Department of Otolaryngology at the University of Rochester or on a password-protected encrypted share drive. The results of any research studies performed with the banked samples may be presented at meetings or in publications without disclosure of subject identity.

Subject Identification, Recruitment and Consent

Study subjects meeting the defined inclusion and exclusion criteria will be recruited from the rhinology clinic at the University of Rochester Medical Center. In addition, patients with a diagnosis of CRS that are status post bilateral sinus surgery but are not currently infected will be offered a flyer outlining the specifics of our study. The flyer will instruct the patients to call our research coordinator for a telephone screening. If eligible, they will be contacted by an investigator for an examination. Eligible patients will also have information about the study printed in their checkout materials via eRecord smartphrase, with instructions to contact [name] prior to taking antibiotics for a flare up. Similarly an eRecord smartphrase will be used to inform PCP that the patient may be study eligible if they present with a CRS flare up.

Treatment options proposed are routinely used for CRS patients. This decreases the risk of any undue influence, as patients would be receiving one of these treatment regimens regardless of their inclusion in the study. Patients electing to participate will undergo an informed consent process by one of the investigators. The study will be explained at length and the consent form will be reviewed with the patient. All questions or concerns will be addressed to the patient's satisfaction. The subject will be given the option of reviewing the consent form at home if desired. The decision to participate or not to participate will not alter their care in any way.

Costs

Costs to the patients will be minimal. The initial visit, nasal endoscopy, and culture are current clinical standards of practice and will be billed to the patient's insurance. The patient will not be charged for follow up visits, repeat cultures, medical supplies for the study, or medications prescribed.

References

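### The sample-size calculation pairs a 90% responder rate with a 20% standard deviation and no alpha, so its 0.9 power does not follow from its inputs and is unsupported for the declared RSDI-change outcome

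*Combined protocol and SAP*

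**What the plan says.** The sample-size justification is in the protocol under Methods, Subjects. It rests on two assumptions. The first is a patient proportion: "90% of patients taking culture-directed oral antibiotics will experience a clinical and statistically significant improvement in Rhinosinusitis Disability Index (RSID) score". The second is the margin: "The non-inferiority limit of topical therapy is 20% of oral therapy". It then concludes: "Using a standard deviation of 20% and a power of 0.9, 26 subjects will be required in each treatment group". Enrolment is set at 35 per group, 70 in total, to cover exclusions and drop-outs.

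The Study Design section declares a continuous outcome: "Change in Rhinosinusitis Disability Index (RSDI) scores will serve as the primary outcome". On its scale it says: "Total scores range between 0 and 120 with high scores indicating greater burden of disease".

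On analysis, the section Data Collection, Analysis and Monitoring says only: "The results will be analyzed at the study's completion". Nowhere does the document state an alpha, its sidedness, a primary test, a responder threshold, an assumed response rate for topical therapy, or a margin or SD in RSDI points.

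**The concern.** The four inputs do not belong to one calculation. A proportion of patients fixes its own variance, so a separate SD of 20% cannot describe a 90% response rate. A mean change in a score does need an SD and a margin, but on the scale of the score, and a percentage of patients is not a mean change.

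This paragraph is the only support for 26 evaluable and 35 enrolled patients per group. As it stands, a reader cannot tell whether the trial has 0.9 power for its primary outcome. In a non-inferiority trial the same margin and alpha also decide the conclusion. Here the margin could be read as 18 percentage points, 20 percentage points or a fraction of the oral arm's mean RSDI change, and alpha is left open.

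**Working it through.** **Inputs.** From Subjects: oral response 90%; limit 20% of oral therapy, which is 0.20 × 90 = 18 points if relative or 20 points if absolute; SD 20%; power 0.9 (z = 1.2816); 26 required and 35 enrolled per group. Assumed, because not stated: alpha one-sided 0.025 (z = 1.960) or 0.05 (z = 1.645); true topical rate equal to oral unless varied below.

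**1. Reproducing the 26.** Non-inferiority of two means, true difference zero: n = 2 (SD/margin)² (z_α + z_β)².

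- Margin 18, SD 20, one-sided 0.025: 2 × (20/18)² × (1.960 + 1.2816)² = 25.94, so 26.
- Margin 18 at one-sided 0.05 gives 22. Margin 20 gives 22 (0.025) or 18 (0.05).
- An equivalence formula with margin 20 and SD 20 also gives 26: 2 × (1.960 + 1.645)² = 25.99.

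Both routes to 26 treat the percentages as means. Which one was used is inferred.

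**2. Is the SD compatible with the 90% rate?** The patient-level SD of a 90% proportion is √(0.9 × 0.1) = 0.30. An SD of 0.20 would belong to a rate of about 95.8%.

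**3. Responder comparison, both arms truly 90%.** Power = Φ( d / √(2 × 0.09 / n) − z_α ). Example: d = 0.18, n = 26, one-sided 0.025 gives Φ(0.18/0.0832 − 1.960) = Φ(0.203) = 0.581.

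| Margin, one-sided alpha | Power, n = 26 | Power, n = 35 | n per group for 0.9 |
|---|---|---|---|
| 18 points, 0.025 | 0.581 | 0.709 | 59 |
| 20 points, 0.025 | 0.671 | 0.796 | 48 |
| 18 points, 0.05 | 0.698 | 0.807 | 48 |
| 20 points, 0.05 | 0.776 | 0.874 | 39 |

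Exact enumeration with the Farrington-Manning test gives 0.51–0.71 with 26 and 0.64–0.83 with 35. With the Wald test it gives 0.64–0.81 and 0.72–0.86.

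**4. If topical is truly better than 90%.** Power = Φ( (d + p_t − 0.90) / √((0.09 + p_t(1 − p_t)) / n) − z_α ). In the row order of the table, 0.9 is reached at p_t = 0.953, 0.942, 0.940, 0.928 with 26, and at 0.934, 0.921, 0.920, 0.907 with 35.

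**5. RSDI change, the declared outcome.** Margin/SD needed for 0.9 = √(2/n) × (z_α + 1.2816). At one-sided 0.025 this is 0.899 with 26 and 0.775 with 35; at 0.05 it is 0.812 and 0.700. The document gives no RSDI margin or SD to compare with these. Two readings that put margin and SD on one scale do reach 0.9, at one-sided 0.025:

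- Margin 18, SD 20: Φ(0.9 / √(2/n) − 1.960) = 0.901 with 26 and 0.964 with 35.
- Margin and SD both 20% of the oral mean change, so margin/SD = 1: 0.950 and 0.987. This requires a mean change of 1/0.20 = 5 SD.

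**The case against.** The strongest reply is that the text never ties the 20% SD to the 90% proportion. For a continuous primary outcome a means formula is the right family, and under it 26 reproduces at a conventional alpha. If margin and SD share one scale, power is 0.901 or 0.950 with 26 per group. The only demonstrated shortfall concerns a responder comparison, which is not the declared primary outcome. It also depends on equal true rates that the plan does not state, and the Background suggests topical therapy may be the more potent option.

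Much of this stands. A reader might infer that 26 is an arithmetic slip, or that the trial is underpowered for its primary outcome. The documents support neither: 26 follows from a recognisable formula, and no RSDI margin or SD exists against which to show a shortfall.

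It does not rescue the paragraph. The favourable means readings need either a 90% patient proportion used as a mean, or a mean change five times its SD. The plan states and justifies neither. The one effect assumption it does state is a response rate, and with both arms at that rate 0.9 is not reached. The plan states no advantage for topical therapy, and the Background also says there is little evidence on its efficacy compared with oral treatment.

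**Conclusion.** The point holds as a mismatch between inputs and endpoint. The calculation fits neither the responder rate it assumes nor, on any stated scale, the outcome declared primary.

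- **Responder comparison.** With both arms truly 90%, power is 58–78% with 26 and 71–87% with 35 (normal approximation; margin 18 or 20 points; one-sided 0.025 or 0.05). Reaching 0.9 would take 39–59 per group, or a topical rate of about 93–95% (26) or 91–93% (35). The result depends on alpha: at one-sided 0.10 with a 20-point margin, 35 per group gives 0.93. The figures for 35 assume no losses, although the extra nine per group are there to absorb them (1 − 26/35 = 26%).
- **RSDI change.** The 0.9 is unsupported, not shown false. At one-sided 0.025 it holds if the margin is at least 0.90 SD with 26 evaluable per group or 0.77 SD with 35, and fails otherwise.

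This must be corrected because a stated power and sample size rest on inputs that cannot be combined.

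**What to change.** Remove the 90% rate and the 20% SD as joint inputs and restate the calculation for the outcome in Study Design. Suggested text, with blanks for the sponsor:

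> The primary comparison is the between-group difference in mean change in RSDI total score. The non-inferiority margin is __ RSDI points (justification: __), the assumed SD of change is __ RSDI points (source: __), and alpha is __ one-sided. Power is __ with 26 and __ with 35 evaluable patients per group.

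If a responder comparison is intended, reconcile the primary outcome in Study Design with the Subjects section, define a responder, state the assumed topical rate, and use the binomial SD. Replace 0.9 with the power delivered: for example, about 58% with 26 and 71% with 35 at an 18-point margin, one-sided 0.025, both arms 90%.

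**Cost.** Neither route requires added enrolment, since each restates the power for the planned numbers. The sponsor must find and justify an RSDI margin and SD that the documents do not contain, and the responder route needs an amended primary outcome. The stated power may become less favourable. If the sponsor chose to keep 0.9 for a responder comparison at equal 90% rates, the 39–59 evaluable per group would exceed the 35 planned.

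### The protocol does not ensure that the randomisation list is concealed from site staff who may screen or telephone patients

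*Combined protocol and SAP*

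**What the plan says.** **Custody and blinding of the list (Study Design).** Once culture data have been reviewed, "A sealed envelope blinded to the investigators selecting either an oral or topical antibiotic will be sent to the participating pharmacy". The assignment behind it is described as follows: "This will be based on a separate key that has been blinded to the investigators that will randomly assign a study participant". The same paragraph then states: "The list will be maintained by the study coordinator". The investigators are the only people said to be blind to the key.

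**Screening (Subject Identification, Recruitment and Consent).** Besides recruitment in clinic, "patients with a diagnosis of CRS that are status post bilateral sinus surgery but are not currently infected will be offered a flyer". For these patients, "The flyer will instruct the patients to call our research coordinator for a telephone screening". The next step is: "If eligible, they will be contacted by an investigator for an examination". An investigator takes consent.

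**Contact after assignment (Study Design).** Study personnel, not further described, telephone the patient to confirm delivery and again about a week later to ask about adherence and side effects. The pharmacy also telephones patients to teach use of the nebulizer. Patients may instead collect their supply at the clinic, where it is labelled Regime A or Regime B and handed over by the PI or by medically qualified staff.

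**Sample database (Sample storage and confidentiality).** The listed fields include "type of antibiotic used, clinical response to therapy and final microbial diagnosis".

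**The concern.** Blinding and allocation concealment are different protections. The double-dummy regimens mask the treatment once it is given. They do not hide the sequence from whoever holds the list. A person who can see the next assignment, and who also has a say in which patients come forward or when, can hasten, delay or discourage a particular patient. The groups may then differ at entry, and no later analysis can reliably repair that.

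The stakes are real in this trial. It is a small two-arm comparison (70 patients, 35 per group) with a non-inferiority aim, and its primary outcome is change in a questionnaire that the patient completes. A caller who knows the arm could also colour conversations about adherence and side effects during treatment. A list kept by working trial staff, with blinding stated for investigators alone, leaves both possibilities open.

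**Working it through.** The plan gives no figure on this point, and its sample-size calculation (26 required per group, 35 planned) is not affected by it. The check is therefore a comparison of the relevant sections.

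1. **Who is blind to the key?** Study Design names the investigators, for both the envelope and the key. Coordinators, callers and dispensing staff are not mentioned.

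2. **Who holds the list?** The study coordinator. Under Molecular Analysis the same role also administers the list that links sample numbers to patients. The holder is therefore part of the working trial team, not an independent party.

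3. **Who meets patients before assignment?** There are at least two routes. Under Subjects, the main one is an approach at ordinary clinic visits. The flyer route adds telephone screening by a research coordinator, and an investigator sees only the callers who pass. The recruitment section also tells eligible patients, in their checkout papers, to get in touch with a contact whose role cannot be seen in the available text.

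4. **When is the arm assigned?** After culture review. The Timeline places consent at week 0, so consent normally comes first. That order prevents assignment before eligibility is known. It does not hide a list that already exists from the person who keeps it.

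5. **What happens between assignment and treatment?** The Timeline has therapy starting at day 3 to 7, and Subjects defines enrollment as including receipt of treatment. A patient who is assigned but never treated is not counted as enrolled. Staff who knew the arm could influence such losses, and the enrolled group would not show it. With clinic pick-up, the prescription reaches the pharmacy afterwards, to restock. Someone on site must therefore learn which regimen is due, and the protocol does not say who tells them.

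6. **What would the text need in order to ensure concealment from site staff?** Any of these would go a long way: (a) the list-holder takes no part in screening, consent, calls or assessment; (b) upcoming assignments are not visible to anyone on site; (c) each assignment is released singly, after eligibility is recorded. The sealed envelope meets (b) for investigators only. Nothing meets (a) or (c). How the sequence is generated is not described.

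7. **What would be needed to show an actual leak?** (i) The two coordinators are one person or share access; (ii) the list shows assignments not yet made; (iii) that person can influence entry. The documents are silent on (i) and (ii), and they limit (iii) through steps 3 and 4.

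8. **The database field.** Both arms receive levofloxacin, so an entry for the antibiotic separates patients only if it records route. The text does not say whether it does, when it is filled, or who can read it.

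**The case against.** The strongest reply is that the plan already has several barriers. The two coordinator titles may denote two people. Telephone screening is an added route, for patients who are not infected at the time. After the call an investigator, who is blind to the key, examines the patient and takes consent. Entry also requires a positive culture sensitive to levofloxacin, and the plan expects about 30 of up to 100 patients approached to prove ineligible on culture. A screener could not be sure whether a caller would be randomised, or at which place on the list. The end-of-treatment endoscopy is done by an otolaryngologist who does not know the arm.

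All of this stands, and it limits the scope for steering. It does not remove the gap. Investigators can see only the flyer patients who are passed on to them, and nothing bars the list-holder from screening or from the follow-up calls. Concealment has to be stated; it cannot be inferred from job titles.

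It is also fair to object that the database field is a weaker matter. A record of past treatment does not reveal the next assignment, and the entry may hold only the drug name. It is at most a secondary point about blinding.

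**Conclusion.** The concern holds as a gap in the safeguards: the protocol does not ensure that allocation is concealed from site staff. This rests on the text alone and needs no assumption about who fills which role. It is a cheap improvement that should be made, and it does not show that the design has failed.

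A reader might go further and infer that the person who screens by telephone can see the next arm, so that allocation is open to recruitment. The documents do not support that. They never say that the two coordinators are one person or share the list, nor that the list shows assignments still to come.

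A reader might also put a size on the bias by supposing that a few likely responders and non-responders change arms. Any number chosen would be arbitrary, and a shift in response rates does not translate into the stated primary outcome, which is change in RSDI score. The likelihood and the size of any bias are both unknown, so none is given here.

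**What to change.** In Study Design, replace the sentence "The list will be maintained by the study coordinator" with a statement to this effect:

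- The list is generated and held off site, either by a pharmacist at the participating pharmacy who does not make the patient instruction calls, or by a statistician with no part in recruitment.
- Nobody who screens, consents, telephones or assesses patients may see it.
- Each assignment is released singly, and only after consent and culture eligibility have been recorded. The same rule applies to clinic pick-up.

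The condition on the pharmacist is needed because the pharmacy itself telephones patients. The new text should also state how the sequence is generated.

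As a secondary safeguard under Sample storage and confidentiality: if the antibiotic field records route, keep it closed to site staff until outcome data are locked.

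The cost is a few sentences, the transfer of the list, and one message to the list-holder before each clinic pick-up. Treatment, sample size and visits do not change.
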